very few children who appeared to use this strategy within trial levels. Additionally, FAM skill was found to still be predictive of math achievement, even when the subset of children who seemingly used a single-dimension strategy was removed from the analysis. In the current study, we used these check trials as well, but did not include them as part of the accuracy scores for test trial across levels. Consistent with prior studies, children scored significantly above chance on check trials within each trial level at both pre- and post-intervention (all $p < .05$).

Number Line Estimation. Children's number line estimation skills were measured by the number-to-position task ([Siegler & Opfer, 2003](#)), which calls for awareness of both numerical and spatial magnitudes. Children were given a box with randomly selected numbers 1 through 10 and a number line that ran from 0 to 10. Children were instructed to place their finger on the number line where the boxed number would appear. The child answered correctly if they pointed exactly or near (1 number above or below) where the number would be on the number line. Scores were total correct responses.

Math Achievement. Overall math achievement was assessed as a standard score produced from the Number Sense subtest of the Woodcock Johnson IV Tests of Early Cognitive and Academic Development (WJ-IV ECAD) ([Schrank & Dailey, 2014, 2015](#)). This subtest is reliable and valid ([Schrank et al., 2015](#)) and requires students to use skills such as counting items on the page, estimating quantities of items in a picture, and identifying numbers to test their numerical skills. Standard scores were calculated and used in analyses.

Executive Functioning Skill. To evaluate students' EF skills, the Minnesota Executive Function Scale (MEFS) ([Carlson & Zelazo, 2014](#)) was used. This assessment is administered on an iPad and asks the child to sort cards into the correct box based on directions given to them by the examiner. This app was created based on the Dimensional Change Card Sort Task (DCCS;

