given that children completed either the number or size trials at post-switch. Overall, we did not find a significant interaction effect for timepoint x condition (Wilks' Lambda $F(3, 105) = .98, p = .591, \eta_p^2 = .02$). We then examined our planned contrasts. First, we examined pre-intervention to post-intervention change in FAM task performance within each condition, and then compared the two experimental conditions to the two control conditions. All of these contrasts yielded null findings, suggesting that the intervention changes we observed were due primarily to differences within the FAM mixed trial level rather than the FAM post-switch trial level.

Potential Transfer Effects. We examined pre-intervention to post-intervention changes in overall math achievement, number line estimation, and EF skills. We continued to covary age and gender, and for the math achievement and NLE analyses, we covaried pretest EF skills as a general skill variable. For overall math achievement, we did not find a significant interaction between timepoint and condition (Wilks' Lambda $F(3, 109) = .61, p = .605, \eta_p^2 = .02$), nor did we find significant differences within either experimental or control groups in their pre- to post-intervention FAM score changes. For NLE scores as the outcome variable, we did not find an overall interaction effect between timepoint and condition (Wilks' Lambda $F(3, 109) = 1.82, p = .618, \eta_p^2 = .02$). For planned contrasts, we did not find any significant differences across specific conditions in change from pre-intervention to post-intervention. Combining the two experimental conditions and the two control conditions for the complex contrast, we found a significant difference between the changes in NLE scores of experimental and control groups (Wilks' Lambda $F(1, 111) = 5.17, p = .025, \eta_p^2 = .04$) such that the experimental conditions overall significantly improved their NLE scores from pre- to post-intervention (NLE Pre-Int total = 1.60, SE = .26; NLE T2 total = 2.07, SE = .29; Wilks' Lambda $F(1, 111) = 4.40, p = .038, \eta_p^2 = .04$), while the control conditions did not (NLE Pre-Int total = 2.33, SE = .28; NLE Post-Int total

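### Scoring number line responses as right or wrong within one unit discards the size of each error and weakens the exploratory NLE analysis; the item count and chance score needed to read the means are not stated

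*Combined protocol and SAP*

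**What the plan says.** Under Measures, Number Line Estimation, the task is described thus: "Children were given a box with randomly selected numbers 1 through 10 and a number line that ran from 0 to 10". The scoring rule is that a response counts as correct if the child "pointed exactly or near (1 number above or below) where the number would be on the number line". The variable carried into the analysis follows: "Scores were total correct responses". The text gives no number of items, maximum score or chance level.

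The Analytic Plan lists NLE among three exploratory outcomes examined for possible transfer. Under Results, Potential Transfer Effects, the experimental conditions are reported as "NLE Pre-Int total = 1.60, SE = .26; NLE T2 total = 2.07, SE = .29". The control conditions start at "NLE Pre-Int total = 2.33, SE = .28" and end at 2.07 (SE .21). The contrast of experimental with control change is "F(1, 111) = 5.17, p = .025".

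The only comparison with chance in the document concerns the FAM task, where "children scored significantly above chance on check trials". None is given for NLE.

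**The concern.** A pointing response on a 0-10 line is a measurement: it has a distance from the target. The rule turns that distance into a yes or no at one unit. Suppose a child shown 3 points at 8 before the intervention and at 4.5 afterwards. The error falls from 5 to 1.5 units, but the item scores zero both times. Improvement outside the window is invisible, and so is improvement inside it.

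A count of hits within a window can also be earned partly by guessing. Without the item count, a reader cannot tell whether a mean near 2 reflects number line skill, chance, or a mixture of able children and children scoring zero. NLE is the only transfer outcome with a result favouring the experimental conditions. Math achievement showed no effect, and on EF only the non-numerical control group improved. How much the NLE score can carry therefore matters to how that result is described.

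**Working it through.** **Reported figures.** For a 1-df test, partial eta squared = F/(F + df2), and p is the upper tail of the F distribution.

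- Contrast: 5.17/(5.17 + 111) = .044, p = .0249 (stated .04, .025).
- Experimental change: 4.40/(4.40 + 111) = .038, p = .038 (stated .04, .038).
- Control change: 1.37/(1.37 + 111) = .012, p = .244 (stated .01, .245).

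These reproduce. The difference in change is (2.07 - 1.60) - (2.07 - 2.33) = 0.73 items.

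**Chance per item.** The inputs are the 0-10 line, targets 1 to 10 equally often, and the one-unit tolerance. The guessing model is an assumption.

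- Uniform pointing along the line: targets 1-9 have a 2-unit window (.2) and target 10 a 1-unit window (.1). The mean is (9 x .2 + .1)/10 = .19.
- Uniform pointing at the whole numbers 0-10: targets 1-9 are hit by 3 of 11 positions and target 10 by 2 of 11. The mean is (27 + 2)/110 = .264.

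**Chance score and distance of each mean from it.** z = (mean - chance)/SE, in the order experimental pre (1.60, SE .26), experimental post (2.07, .29), control pre (2.33, .28), control post (2.07, .21). The item count is assumed.

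| Items | Chance at .19 | z | Chance at .264 | z |
|---|---|---|---|---|
| 5 | 0.95 | 2.50, 3.86, 4.93, 5.33 | 1.32 | 1.1, 2.6, 3.6, 3.6 |
| 6 | 1.14 | 1.77, 3.21, 4.25, 4.43 | 1.58 | 0.1, 1.7, 2.7, 2.3 |
| 8 | 1.52 | 0.31, 1.90, 2.89, 2.62 | 2.11 | -2.0, -0.1, 0.8, -0.2 |
| 10 | 1.90 | -1.15, 0.59, 1.54, 0.81 | 2.64 | -4.0, -2.0, -1.1, -2.7 |
| 12 | 2.28 | -2.62, -0.72, 0.18, -1.00 | 3.16 | -6.0, -3.8, -3.0, -5.2 |

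With ten items and uniform pointing, no mean is distinguishable from chance. With eight items, both control means are above it; with twelve, the experimental pre-test mean is below it. With whole-number pointing and ten items, all four means lie below chance.

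**Can the item count be bounded?** A score between 0 and N has variance of at most mean x (N - mean). Treating the SE as raw, the experimental post-test variance is .29² x 62 = 5.21. Then 5.21 ≤ 2.07(N - 2.07) gives N ≥ 4.6. Five items would need 5.21/(2.07 x 2.93) = 86% of the maximum variance, with nearly every child at 0 or 5. Very short tests are therefore unlikely, but the range above stays open.

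**Do the scores look like pure guessing?** Ten-item guessing has SD √(10 x .19 x .81) = 1.24. The SEs imply SDs (SE x √n, n = 62 and 54) of 2.05, 2.28, 2.06 and 1.54. Results also states that pre and post scores on each measure were significantly correlated, which independent guessing would not produce.

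**Would guessing create a false contrast?** In 20,000 simulated trials with every child guessing over ten items at .19, comparing change in 62 against 54 children rejected at the 5% level 5.1% of the time.

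**What does the cut-off cost?** In a simulation with normal pointing error around the target and ten assumed items, mean absolute distance roughly doubled the standardised difference obtained from the count. The gain is smaller if children differ in precision, so this shows direction and rough size only.

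**The case against.** The strongest reply is that NLE is openly exploratory, that the results heading calls the transfer effects potential, and that the supplied text has no conclusion section asserting transfer. The scoring rule is stated plainly, and a coarse score lowers sensitivity without biasing a randomised comparison. The check-trial test against chance was there to detect single-dimension responding on a two-choice task, so the absence of a similar test for NLE is not an inconsistency. Table 1, cited for descriptive statistics, is not in the text available here and may show a score range.

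All of this stands, and it limits the point to scoring and reporting.

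A reader might go further and infer that the means sit at the guessing level, so that the contrast is noise. The documents do not support this. The first step needs an item count they do not give, and it changes with the guessing model. The spread and the pre-post correlation do not fit pure guessing, although stable pointing habits could produce both, so they do not prove skill either. The second step does not follow even if the first is granted, because the simulated error rate under pure guessing stayed near 5%. Nor is it sound to bar the word transfer unless scores exceed chance: that would make a test of absolute level the gate for a comparison of change between randomised groups.

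**Conclusion.** The point holds as a scoring and reporting weakness in an exploratory outcome. Cutting each response at one unit discards the size of the error and lowers the sensitivity of the NLE analysis. The loss may be substantial: about half the standardised difference in an illustrative model that assumes ten items and normal error.

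The closeness of the means to 1.9 is a caution that rests on two assumptions, about ten items and uniform pointing. Across 5 to 12 items and the two guessing models, the chance score runs from 0.95 to 3.16, which spans all the reported means. The SDs and the bound on item count treat the published SEs as raw; they may be model-adjusted. Nothing here shows that the contrast at p = .025 is a false positive.

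**What to change.** If pointed positions were stored, rescore NLE as the mean absolute distance between the pointed position and the target. Rerun the same repeated-measures model and contrasts, and report the result beside the count score.

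If only right/wrong was stored, state the number of items and the chance score with the guessing model behind it. Report the NLE scores against chance, and describe the exploratory NLE contrast with that limitation.

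The cost is a small reanalysis of existing data. Rescoring is possible only if positions were recorded, and the NLE result may change in either direction.

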Zelazo, 2006). The child either advances to the level above their previous level or goes to a level below, depending on the correctness of their choices. There are 7 levels that the child could attempt, with each level increasing in difficulty. Each level uses a different rule for how the cards should be sorted and can include tasks like sorting by size, color, and shape depending on the level of difficulty. As the levels increase, children must use EF skills to shift their focus between multiple characteristics in order to sort the cards correctly. A standard score was produced from the accuracy of the child's answers and from their response time, and this score was used in the analysis.

Books. This design utilized a pretest-intervention-posttest design with four one-on-one sessions with an experimenter at the child's school, and compared improvement in FAM skill across four conditions: size-to-number comparisons, mixed comparisons, traditional counting, and non-numerical (See Figure 2 for sample pages from each condition).

The size-to-number comparisons and mixed comparisons were experimental conditions, while the traditional counting and non-numerical conditions served as controls. The size-to-number condition books first included 10 question pages asking children to attend to the size of objects. Following the first set of question pages were 10 more question pages asking children to attend to the number of objects. Alternatively, the mixed condition included 20 question pages that alternated between asking children to attend to the size of objects and the number of objects in an arbitrary order. In both experimental conditions, each question page was followed by a feedback page either praising the child for answering correctly, or directing the child to the correct answer while emphasizing the incongruity between the size and number of objects. Including two experimental conditions enabled us to examine children's ability to switch from repeatedly focusing on one dimension of magnitude to repeatedly focusing on another (size-to-

number) and children's ability to continuously switch back and forth between dimensions (mixed). We expected that each of the experimental conditions would result in improvement on the FAM task at post-test; however, we did not have a prediction as to if one experimental condition would be more successful than the other.

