word count on each page was similar across conditions. In the traditional counting, size-to-number, and mixed conditions, the number of objects on each side of the page followed three different simplified ratios: 1:3, 2:3, 1:2. Each page followed these ratios using between 2 and 10 objects on each side of the page, to make sure that the numbers were within the range of numbers which preschool age children are familiar with. The size-to-number and mixed book conditions also varied the total area of objects on each side of each page based on these same three simplified ratios. The ratio of the total area on each side was the inverse of the ratio of total objects on each side. For instance, in a trial where the left side of the page contained 2 objects and the right side contained 4 objects (1:2 ratio), the objects on the left side had a total area that was twice the total area of the objects on the right side (See Figure 2 to view sample pages for each condition). The correct answer was distributed evenly across the right and left sides of pages.

Power Analysis and Exclusion Criteria. A power analysis conducted in G*Power for a 2 (timepoint: pre-intervention and post-intervention) x 4 (condition: counting, mixed, non-numerical, size-to-number) ANOVA, and a within-between interaction, revealed a necessary sample size of 84 participants for the study (21 participants per group). We assumed a medium effect size ($\eta_p^2 = .02$), 2 timepoints, 4 between-participants groups, and a correlation between pre-intervention and post-intervention of $r = .4$ for the power analysis. We initially recruited 169 participants for the study, knowing that school absences during a short-term weeklong study would likely significantly reduce the final sample size. There were 116 participants in the final sample size (Size-to-Number condition $n = 37$, Mixed condition $n = 25$, Counting condition $n = 30$, Non-numerical condition = 24) who were present at all pre-intervention and post-intervention assessments and book reading sessions and had complete assessment data. We randomly

assigned children within each condition to either the number first FAM assessment or the size first FAM assessment (number first n = 61, size first n = 55). Participant exclusions were primarily due to school absences (n = 28), children not wanting to participate in one or more assessments (n = 13), developmental delays (n = 1), and technical errors with the online data collection system (n = 11).

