Analytic Plan

Primary Analyses. Our primary research question was if children in the experimental FAM conditions significantly improved their FAM skills from pre-intervention to post-intervention. We did not have a prediction about whether one of the experimental FAM conditions would outperform the other experimental FAM condition. We conducted a repeated-measures ANOVA with timepoint (pre-intervention and post-intervention) as the within-participants factor and condition (size-to-number, mixed, counting, non-numerical) as the between-participants factor, controlling for age, gender, and EF skills. We analyzed planned contrasts for the condition by timepoint interaction that included a complex contrast testing for differences between the experimental (mixed and size-to-number) and control groups (counting and non-numerical) in their FAM task changes across timepoints, as well as simple contrasts comparing FAM changes across timepoints within each of the four conditions. We first examined the FAM mixed trials as our outcome of interest given that children were randomly assigned to complete different versions of the FAM task that varied in if the number or size trials were the pre-switch and post-switch trial levels. This mixed level was the trial level that was the same across all conditions. However, we also ran these analyses using the combined FAM post+mixed accuracy variable as this has been the variable used in prior correlational analyses, and we included FAM version as a covariate.

Exploratory Analyses. To explore potential differences in findings across number and size trials in the FAM task, we repeated our primary analyses, but with the number and size trials and pre- and post-intervention scores as the within-participants factor, controlling for FAM version and other covariates used in prior analyses. We also ran the same repeated-measures ANOVA with three other outcomes (global math achievement, number line estimation, and EF skills) to assess for potential transfer effects.

Results

Descriptive Statistics and Correlations

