compared to control groups (counting, non-numerical). Overall, we did not find a significant interaction effect for timepoint x condition (Wilks' Lambda $F(3, 109) = .96, p = .41, \eta_p^2 = .03$). We then tested our planned comparisons, as they were driven by our hypothesis that FAM ability can be improved through intervention. Prior studies examining the relevance of planned comparisons supported this decision by encouraging researchers to perform planned comparisons regardless of the outcome of the ANOVA analysis, especially when those comparisons are supported by previous findings or theory ([Ruxton & Beauchamp, 2008](#))

First, we examined pre-intervention to post-intervention change in FAM task performance within each condition, and then compared the two experimental conditions to the two control conditions. Children significantly improved their FAM task performance from pre-intervention to post-intervention within the two experimental groups, mixed (Wilks' Lambda $F(1, 109) = 8.65, p = .004, \eta_p^2 = .07$) and size-to-number (Wilks' Lambda $F(1, 109) = 4.77, p = .031, \eta_p^2 = .04$) (See Figure 3). Children did not significantly improve their FAM task performance in the two control group conditions, counting (Wilks' Lambda $F(1, 109) = .54, p = .463, \eta_p^2 = .01$) and non-numerical (Wilks' Lambda $F(1, 109) = 1.77, p = .186, \eta_p^2 = .02$) (See Figure 3). These findings also held when comparing the two experimental conditions to the two control conditions such that children in the two experimental conditions significantly improved their performance (Wilks' Lambda $F(1, 111) = 12.90, p < .001, \eta_p^2 = .10$) (See Figure 4) while children in the control conditions did not (See Figure 2) (Wilks' Lambda $F(1, 111) = 2.11, p = .150, \eta_p^2 = .02$) (See Figure 4).

FAM Post + Mixed Trial Level Outcomes. We also conducted the same analyses with the exception of the outcome variable being the FAM Post+Mixed task performance as this variable has been used in prior FAM studies (Fuhs et al., 2021). We included FAM version as a covariate

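### The plan predicts that each experimental book type improves FAM, but no test sets either arm alone against controls; the per-arm statements rest on uncontrolled pre-post change

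*Combined protocol and SAP*

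**What the plan says.** **Prediction.** Measures, Books, on the two experimental conditions: "We expected that each of the experimental conditions would result in improvement on the FAM task at post-test". The Analytic Plan (Primary Analyses) words the main question the same way: "Our primary research question was if children in the experimental FAM conditions significantly improved their FAM skills from pre-intervention to post-intervention". The Results (Primary Analyses, FAM Mixed Trial Level Outcomes) add a comparator: the experimental conditions were predicted to improve "compared to control groups (counting, non-numerical").

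**Planned tests.** The Analytic Plan lists two kinds of contrast on FAM change. The first is "a complex contrast testing for differences between the experimental (mixed and size-to-number) and control groups (counting and non-numerical"). The second is "simple contrasts comparing FAM changes across timepoints within each of the four conditions". The model is a timepoint-by-condition repeated-measures ANOVA, "controlling for age, gender, and EF skills".

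**Reported.** For the FAM mixed trials the omnibus interaction is F(3,109) = .96, p = .41. The Results then state: "Children significantly improved their FAM task performance from pre-intervention to post-intervention within the two experimental groups", with p = .004 for mixed and p = .031 for size-to-number. They set this beside non-significant changes in counting (p = .463) and non-numerical (p = .186).

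**The concern.** The prediction is about each arm, but the controlled comparison is about the two arms together. A pooled contrast, even a significant one, cannot show that both book types work, because one effective arm can produce it.

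The within-arm tests are arm-specific but have no control. Children take the FAM assessment on day one and again on day four (Procedure), with feedback on its practice trials (Measures, FAM Skill). Gain from repeating the task, or from time spent with experimenters, therefore counts as improvement. The document says the non-numerical condition is there to control for the second of these, but the per-arm tests do not use it. A significant change in one arm beside a non-significant change in another is not a test of the difference between them.

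At stake is whether readers may conclude that both book types raise FAM skill. An arm with nothing beyond retest gain could be declared improved, and the effect of one arm could be credited to both.

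This is not the mixed versus size-to-number comparison, on which the document makes no prediction.

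**Working it through.** **Inputs.**
- Analysed arm sizes (Power Analysis and Exclusion Criteria): size-to-number 37, mixed 25, counting 30, non-numerical 24; total 116.
- Within-arm F(1,109) (Results, FAM Mixed Trial Level Outcomes): mixed 8.65, size-to-number 4.77, counting .54, non-numerical 1.77.
- Omnibus F(3,109) = .96. Error df: 116 - 4 conditions - 3 covariates = 109.
- Alpha is not stated for the primary analysis; two-sided .05 is assumed.

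**Step 1: gain per arm.** In units of the residual SD of change, gain = sqrt(F/n), assuming that covariate adjustment leaves the effective n of each arm unchanged.
- Mixed: sqrt(8.65/25) = 0.588
- Size-to-number: sqrt(4.77/37) = 0.359
- Counting: sqrt(.54/30) = 0.134
- Non-numerical: sqrt(1.77/24) = 0.272

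**Step 2: reproduce the printed omnibus F.** The n-weighted mean gain is 0.332. The sum of n × (gain - mean)² is 1.639 + 0.027 + 1.176 + 0.088 = 2.930. Dividing by 3 gives F = 0.98, against .96 printed. An F value does not show direction, so the signs of the control changes were checked: with one or both negative, the omnibus F would be 2.57 to 4.37. Both control arms therefore also rose.

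**Step 3: a bound that needs no reconstruction.** A one-df contrast of condition changes in the four-condition model cannot exceed 3 × the omnibus F. Here 3 × .96 = 2.88, so p is about .093 or larger. The critical F(1,109) at .05 is 3.93. This holds whatever the signs or covariate adjustment.

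**Step 4: each arm against the mean of the two controls.** Control mean = (0.134 + 0.272)/2 = 0.203. SE = sqrt(1/n_arm + (1/30 + 1/24)/4), df 109.

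| Arm | Difference (SD) | SE | t | 95% CI | p | Holm p |
|---|---|---|---|---|---|---|
| Mixed | 0.588 - 0.203 = 0.385 | 0.242 | 1.59 | -0.10 to 0.87 | .115 | .23 |
| Size-to-number | 0.359 - 0.203 = 0.156 | 0.214 | 0.73 | -0.27 to 0.58 | .467 | .47 |

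Weighting the controls by n instead gives p = .107 and .444.

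**Step 5: how easily a within-arm test passes on retest gain alone.** The n-weighted control gain is (30 × 0.134 + 24 × 0.272)/54 = 0.195 SD, which is 54% of the size-to-number gain (0.195/0.359). Suppose an arm's true gain were exactly this and all of it were retest. From a noncentral t with 109 df, its within-arm test would then declare improvement about 22% of the time with n = 37 and 16% with n = 25, against a nominal 2.5% in that direction.

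The control gain is itself uncertain: 0.195 ± 1.982/sqrt(54) gives about -0.07 to 0.46 SD. Across that interval the rates run from about 1% to 80% (n = 37) and 1% to 63% (n = 25). They illustrate the mechanism and do not estimate its size.

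**The case against.** **The wording of the prediction.** Both the Books statement and the primary question speak of improvement from pre to post with no comparator, and the within-condition contrasts test exactly that. The controlled prediction in the Results names the experimental conditions together, which fits the pooled contrast. This stands in part: the document nowhere spells out a hypothesis of each arm against controls, so the point is a gap between claim and test and not an outright contradiction. It does not remove the gap. The Books section describes the design as comparing improvement across the four conditions, and the control arms have no other purpose.

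**Controls are not ignored.** The omnibus interaction is a randomised between-group test and is reported first, and the Results say that children improved within groups. That is fair, but the omnibus test is not arm-specific and was null.

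**Retest gain is not established.** Pre-switch and post-switch scores fell slightly (Descriptive Statistics), feedback was limited to two practice trials per level, and counting children practised a related judgement. This stands, and it is why the 22% and 16% figures are only illustrative.

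**A tempting stronger reading.** A reader might infer that both arms fail against controls, or that the books do not work. The documents do not support this. They report no such test, and the interval for mixed reaches 0.87 SD. The smallest difference detectable with 80% power is about 0.68 SD for mixed and 0.60 SD for size-to-number.

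**A more basic gap lies nearby.** The planned pooled FAM contrast appears in the Results only as two within-group tests, although the between-group F is given for number line estimation. That is true and related, but reporting it would still not answer a per-arm prediction.

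**Conclusion.** The concern holds as a gap between what is predicted and what is tested. No analysis compares mixed alone, or size-to-number alone, with controls, and the per-arm statements rest on uncontrolled change in a repeated task.

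The firmest result is the bound in step 3. It depends only on the printed omnibus F and the assumed two-sided .05, and it means that neither arm-versus-control contrast in that model can be significant. The estimates in step 4 depend also on the effective-n assumption, which the close match to the printed omnibus F supports. They are best read as positive but imprecise: the data neither establish an effect of either book type over controls nor rule one out.

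**What to change.** In the four-condition model, report two one-df timepoint-by-condition contrasts: mixed versus the mean of the two controls, and size-to-number versus the mean of the two controls. Give estimates, 95% CIs and Holm-adjusted p-values over the two. Because results are already reported, label both as added after the results were known, not as planned.

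Label the four within-condition pre-post tests as descriptive. Reword the FAM Mixed Trial Level Outcomes text so that no arm is said to have improved FAM relative to controls on the strength of its within-arm test.

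The cost is two contrast statements in a model already fitted, plus wording; no new data are needed. The downside is that the per-arm claim becomes less favourable, and each contrast is less precise than the pooled one (SE 0.242 and 0.214 SD, against 0.188 SD for the pooled contrast with equal arm weights).
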